##### Sequence 2:

- Period 1: 300 mg ARN-75039 with excipients in tablet form (comparator)
- Period 2: 300 mg neat ARN-75039 in HPMC capsules (reference product)

Written informed consent for study participation will be obtained before any study-related procedures or assessments are performed. All potential participants will be screened for potential participation, and those meeting all eligibility criteria will be offered participation in the study.

Participants will be admitted to the study site on the morning of Day -1, randomized to Period 1 study drug administration on Day 1, and will remain on site until study completion at Day 15. Participants will receive the randomized study drug in the morning following a meal. Participants will be dosed on Day 1 and Day 8 with a 7-day wash out period between the two dosing days. PK assessments will be performed according to the SOA ([Table 1](#)).

Participants that withdraw from active treatment or are terminated from the treatment period will undergo an Early Termination (ET) visit.

Participation in the study will be conducted in the following 5 defined periods, with a total study duration of approximately 57 days:

- **Screening Period:** The Screening Period begins when the informed consent form (ICF) is signed. During this period, participants will undergo baseline assessments to determine eligibility for study participation. The Screening Period duration will be up to 21 days; it will end after all evaluations required to meet eligibility have been completed. If a participant meets all eligibility criteria, they will be offered enrollment into the study.

- **Admission to the Study Center:** Participants will be admitted to the study site in the morning on the day prior to dosing of period 1 (Day -1) and will remain at the study site until study completion (Day 15). Upon admission to the study site, participants will be randomized into the study on Day 1 after the confirmation of eligibility.
- **Treatment Period:** This study consists of two treatment days separated by a 7-day washout period. The first treatment day will begin on Day 1 of Period 1 with administration of the first dose of study drug. The second treatment day will occur on the first day of Period 2 (Study Day 8). Following the dosing of the study drug on each treatment day, fifteen venous blood samples will be withdrawn via an indwelling cannula or by venipuncture at regular time intervals. Subjects will be discharged on Day 15.

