- **End of Active Treatment (Day 15 Discharge Visit or Early Termination Visit):** Upon successful completion of active treatment, participants will be discharged from the study site on Day 15. The Day 15 Discharge Visit will include the completion of safety assessments, such as a physical examination, vitals, ECG recording, adverse event review, and clinical laboratory tests. Participants who complete both dosing days will be encouraged to complete all study visits. Participants who do not complete all study visits or terminate early from the study will be asked to complete the Early Termination Visit within 1 day after withdrawal from the study.
- **Day 36 Telephone Follow Up Phone Call:** Participants will be contacted by phone on Day 36—i.e., 28 days following the last study dose administered on Day 8. The purpose of this follow-up call is to assess for any adverse events.

If a participant has a study drug-related Grade > 1 TEAE during the Treatment Period, study drug dosing may be discontinued for that participant following discussion between the Investigator and Sponsor Medical Monitor. These participants will not be replaced. If a subject has a study drug-related Grade 1 TEAE during the Treatment Period, study drug dosing may also be discontinued for that subject per the Investigator's discretion. However, these subjects may be replaced at the Sponsor's discretion. Discontinued participants experiencing a study drug-related TEAE will be asked to complete follow up study visits through the Day 36 Phone Call Follow Up.

If a participant terminates early for a reason other than a study drug-related TEAE during the Treatment Period, the participant may be replaced. These participants will also be asked to complete follow up study visits through the Day 36 Phone Call Follow Up, unless they terminated their participation in the study prior to dosing. Study drug dose level modifications or dosing administration deviations outside the protocol-specified windows are not permitted during the Treatment Period.

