### 4.1. Participant Inclusion Criteria

Participants meeting all the following criteria are eligible for study participation:

1. Is male or female, age 18 to 45 years, inclusive, at Screening.
2. Body mass index (BMI) between 18 and 35 kg/m^2, inclusive, at Screening.
3. In good general health, determined by no clinically significant findings in the opinion of the Investigator from medical history, physical examination, 12-lead ECG, clinical laboratory findings, and vital signs at Screening and Day -1 or 1.
4. Hemoglobin, hematocrit, white blood cell count, absolute neutrophil count, and platelet count results within the laboratory reference range at Screening or without clinically significant abnormalities in the opinion of the Investigator; participants with Gilbert's disease with associated abnormalities of liver function tests are eligible for enrollment. Tests may be repeated at the discretion of the Investigator to confirm abnormalities.
5. Estimated glomerular filtration rate (eGFR) based on the Chronic Kidney Disease Epidemiology Collaboration (CKD-EPI) equation of  $\geq 80$  mL/min/1.73 m^2 at Screening.
6. Females of childbearing potential must practice effective contraception per national regulatory guidelines for clinical trials from Screening (see Section 5.6.2), throughout the study, and for 60 days after the last dose of study drug.
7. Females must have a negative pregnancy test at Screening and within 24 hours prior to dosing of study drug; for post-menopausal participants, a blood sample will also be tested for estradiol and follicle stimulating hormone (FSH) to confirm post-menopausal status based on reference laboratory ranges for post-menopausal status. Surgically sterile females are eligible; however, proof via medical records will be required.
8. Males must agree to not donate sperm and to use condom and spermicide in combination with any of the means of contraception for their female partners detailed in Section 5.6.2 during sexual intercourse from the time of the first study drug administration and for

90 days following the last dose of study drug. Females must agree not to donate eggs from the time of the first study drug administration and for 60 days following the last dose of study drug.

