### **5.6.2. Contraception**

Individuals of reproductive potential who are (hetero) sexually active must be willing to use effective contraception from Screening through 60 days after the Day 15 visit. (Individuals who are at least 1 year post-menopausal are not of reproductive potential.) Acceptable means of contraception include:

- Individuals who have been surgically sterilized.

- Females of reproductive potential: diaphragm, injectable, oral/patch contraceptives for a minimum of 6 weeks, contraceptive sponge, implant, or intrauterine device in use prior to enrollment, with use of condom for their male partners.
- Males: Males must agree to not donate sperm and to use condom and spermicide in combination with any of the above means of contraception for their female partners during sexual intercourse from the time of the first study drug administration and for 90 days following the last dose of study drug.
- All individuals: abstinence may be an acceptable means of contraception as long as the individual consents to initiate immediate use of double barrier protection for the duration of the study should (hetero) sexual intercourse occur.

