**Table 4: Clinical Laboratory Tests**

Hematology: 
 
• Hematocrit
 
• Hemoglobin
 
• Platelet count
 
• RBC count
 
• WBC count – with differential
 
	Serum Chemistry: 
 
• Glucose
 
• BUN
 
• Creatinine
 
• Total bilirubin
 
• AST
 
• ALT
 
• GGT
 
• Alkaline phosphatase
 
• Creatine kinase
 
• Total protein
 
• Lactate dehydrogenase
 
• Direct bilirubin
 
• Total bilirubin
 
• Sodium
 
• Potassium
 
• Total CO2
 
• Chloride
 
• Calcium
 
• Inorganic phosphate
 
• Magnesium
 
• eGFR
 

Coagulation: 
 
• PT/INR
 
• PTT
 
	
Urinalysis: 
 
• Bilirubin
 
• pH
 
• Specific gravity
 
• Protein
 
• Leukocytes
 
• Urobilinogen
 
• Glucose
 
• Nitrates
 
• Ketones
 
• Blood
 
• Microscopic urine analysis
 
	
Urine Drug Screen: 
 
• Amphetamines
 
• Barbiturates
 
• Opiates
 
• Benzodiazepines
 
• Cocaine metabolites
 
• Cannabinoids
 
	
Pregnancy Testing: 
 
• Serum hCG – at Screening
 
• Urine hCG – at the time of study center admission and Day 15 Discharge or ET
 
	Post-Menopausal Status Testing: 
 
• FSH
 
• Estradiol
 

Alcohol Screening: 
 
• Breath alcohol test
 
	

Abbreviations: ALT = alanine aminotransferase; AST = aspartate aminotransferase; BUN = blood urea nitrogen; CO2 = carbon dioxide; eGFR = estimated glomerular filtration rate; FSH = follicle-stimulating hormone; GGT = gamma-glutamyl transferase; hCG = human chorionic gonadotropin; INR = international normalized ratio; PT = prothrombin time; PTT = partial thromboplastin time; RBC = red blood cell; WBC = white blood cell.

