### **6.12.5. Pregnancy**

Should a pregnancy occur in a female participant or the partner of a male participant, it must be reported and recorded on the pregnancy form. Pregnancy in itself is not regarded as an AE unless there is a suspicion that an investigational product may have interfered with the effectiveness of a contraceptive medication.

The outcome of all pregnancies (spontaneous miscarriage, elective termination, normal birth or congenital abnormality) must be documented, and any live births are to be followed for 1 month.

All reports of congenital abnormalities/birth defects are SAEs. Spontaneous miscarriages should also be reported and handled as SAEs. Elective abortions without complications should not be handled as AEs.

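### After discharge or early termination the protocol schedules no pregnancy test and no pregnancy question, although it requires every participant and partner pregnancy to be reported and its contraception windows run well past the last contact.

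*Protocol*

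**What the plan says.** - **Confinement.** Under Protocol Section 3.1, participants are admitted on Day -1 and "will remain on site until study completion at Day 15".
- **Pregnancy tests.** Sections 6.8 and Table 4 give a serum test at Screening and urine tests "at the time of study center admission and Day 15 Discharge or ET". Table 1 marks none later.
- **Last contact.** Section 3.1: "Participants will be contacted by phone on Day 36—i.e., 28 days following the last study dose administered on Day 8". It continues: "The purpose of this follow-up call is to assess for any adverse events". The synopsis describes the call in the same way. In Table 1 of both the protocol and the SAP, the only row marked for this call is adverse events.
- **Status of pregnancy.** Section 6.12.5: "Pregnancy in itself is not regarded as an AE". The one stated exception is suspected interference by the product with a contraceptive medication.
- **Reporting duty.** For a pregnancy in a female participant or a male participant's partner, the same section says "it must be reported and recorded on the pregnancy form". It also requires the outcome to be documented and live births to be followed for a month, and it treats miscarriages and congenital abnormalities as serious adverse events (SAEs).
- **Contraception windows.** Inclusion criterion 6 requires contraception for women of childbearing potential from Screening, "throughout the study, and for 60 days after the last dose of study drug". Section 5.6.2 opens with a different end, 60 days counted from the Day 15 visit. For men it requires precautions "from the time of the first study drug administration and for 90 days following the last dose of study drug".

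**The concern.** The protocol treats conception as a matter of concern for weeks after the last dose and sets a firm duty to report pregnancies and follow their outcomes. The scheduled procedures do not feed that duty once participants go home. The last test falls on the day confinement ends, so it cannot show a conception that happens afterwards. The one later contact has a scope that, on the protocol's own definition, leaves out pregnancy in itself. Partner pregnancies have no scheduled enquiry at any time.

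What is at stake is participant and fetal safety follow-up. Miscarriage and congenital abnormality are SAEs under Section 6.12.5, so a pregnancy that nobody asks about can become an SAE that nobody records. If no pregnancy comes to light, the sponsor cannot tell whether none occurred or none was asked about.

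**Working it through.** The check is study-day arithmetic for a participant who takes both doses and is discharged on Day 15.

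**Inputs.** Last dose Day 8; last test and discharge Day 15; call Day 36 ± 2 days (Section 3.1, Table 1, Table 4). Windows: last dose + 60 days (criterion 6), Day 15 + 60 days (Section 5.6.2), last dose + 90 days (men, Section 5.6.2).

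**The plan's own figures.** 8 + 28 = Day 36, as stated. 21 screening days + 36 = 57 days, matching the stated total duration.

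**After discharge.** Window end minus 15 gives the days after the last test (for men, after discharge). Window end minus 36 gives the days after the call, and the range uses Day 38 and Day 34.

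| Window | Ends | Days after Day 15 | Days after the call |
|---|---|---|---|
| Women, criterion 6 | 8 + 60 = Day 68 | 68 − 15 = 53 | 68 − 36 = 32 (30 to 34) |
| Women, Section 5.6.2 | 15 + 60 = Day 75 | 75 − 15 = 60 | 75 − 36 = 39 (37 to 41) |
| Men | 8 + 90 = Day 98 | 98 − 15 = 83 | 98 − 36 = 62 (60 to 64) |

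Scheduled pregnancy tests or questions in the Day 15 column: none.

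**Before admission.** The female window opens at Screening, as early as Day -21. There is no Day 0, so Day -21 to Day -1 is 20 days. The Day 15 test falls 35 days after Day -21 (21 + 15 − 1) and 15 days after Day -1 (1 + 15 − 1). The Day -1 and Day 15 tests can therefore pick up conceptions between Screening and admission.

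**Share of each window after Day 15.** Women: 53/88 = 60% (criterion 6; 21 + 68 − 1 = 88 days) or 53 + 7 = 60 of 95 days = 63% (Section 5.6.2; 21 + 75 − 1 = 95). Men, from first dose: 83/97 = 86% (98 − 1 = 97).

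**People concerned.** The enrollment goal of 30% to 50% women among 16 gives 0.30 × 16 = 4.8 to 0.50 × 16 = 8, so at most 5 to 8 women, and 8 to 11 men through their partners. These are upper bounds. Surgically sterile and post-menopausal women are eligible, and Section 5.6.2 applies to people of reproductive potential who are heterosexually active, with abstinence allowed.

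**The case against.** A reader might infer that no scheduled step can detect any pregnancy conceived in the contraception window. The documents do not support that: the tests on Day -1 and Day 15 cover conceptions between Screening and admission. The gap is confined to the time after discharge or ET.

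A reader might also infer that the reporting duty cannot be met, or that the call can never bring a pregnancy to light. That too goes further than the text allows. Section 6.12.4 collects adverse events partly by an open question, so a pregnancy may be mentioned in answer and would then have to be recorded. A pregnancy under the contraceptive-interference exception is an adverse event, and miscarriage and congenital abnormality are SAEs, so these fall within the call's scope. Section 6.12.7 also provides for related SAEs found after the last follow-up visit. What stands is that pregnancy is not actively prompted for.

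Three further points have force.

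- **Consent form.** The consent pages and the pregnancy form are not among the documents available here. They may already tell participants to report a pregnancy. The scope of the call is the same either way.
- **Limits of the call.** It would be tempting to count all 21 days from Day 15 to Day 36 as covered once a question is added. Recognising a pregnancy takes time. If that takes 14 to 21 days (an assumption; the documents give no figure), the call would reveal only conceptions in the first 7 to 0 days after discharge. The question alone is not enough.
- **Analysis.** Pregnancy is not an endpoint and the SAP plans no summary of it, so no planned result changes.

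**Conclusion.** The point holds for conceptions after discharge or ET. In that period the protocol has a reporting and outcome duty but no scheduled test or enquiry behind it. For a participant who takes both doses the unprompted period lasts 53 or 60 days for women, depending on which of the two inconsistent statements applies, and 83 days for men. All three windows outlast the Day 36 call. The number of people concerned is small and the figures above are upper bounds. The weakness lies in active ascertainment; the duty itself is clearly stated.

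The conclusion rests on the protocol and SAP text alone. A self-report instruction in the consent form would lessen the gap but would not put pregnancy within the scope of the call. The change is worth making because it serves participant and fetal safety at almost no cost.

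**What to change.** 1. In Section 3.1 and the synopsis, widen the purpose of the Day 36 call to include asking about pregnancy in the participant or in a male participant's partner. Mark this in the Day 36 column of protocol Table 1. The SAP's copy of the table needs no change for any analysis.
2. Because some pregnancies will not be known by Day 36 and the windows end 32 to 62 days after it, confirm that participants are told at Day 15 or ET to report any pregnancy until their contraception period ends. If the consent form does not already say so, state it in Section 6.12.5.
3. Reconcile the end of the female contraception window between inclusion criterion 6 (Day 68) and Section 5.6.2 (Day 75).

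The cost is one question on a call that is already made, one table mark and a few sentences. No visit or test is added. The downside is that a few reports may arrive, and need follow-up, after the last scheduled contact.

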### 3.2. Justification for the Study Design

A randomized, comparative, crossover study was selected to eliminate participant variation and to improve precision of the PK characteristics of both study drug formulations with a smaller sample size. To compensate for the long half-life of the study drug and the relatively short washout period, additional PK timepoints were included to aid in modeling of the study drug clearance and elimination.

This clinical study is being performed in healthy participants to avoid interference with the results from disease processes and other drugs. Medications, substances, and food products that may interfere with the assessment of the PK profile of ARN-75039 are prohibited during study participation.

### **3.3. Number of Participants**

The sample size of 16 evaluable participants proposed for this study was not based on statistical analysis assessments but is judged to provide a sufficient dataset to be able to make direct comparisons in pharmacokinetic parameter estimates between the reference and test groups in this clinical study. Participants withdrawn due to a study drug-related Grade >1 TEAE will not be replaced. Participants who are withdrawn due to a study drug-related Grade 1 TEAE may be replaced. Participants who are withdrawn due to a reason other than a study drug-related TEAE during the Treatment Period may be as necessary to obtain 16 evaluable participants at the end of the clinical study.

### **3.4. Study Completion**

The site will complete the Study Termination page of the electronic case report form (eCRF) which will mark the completion of the participant's participation in the study.

The date of termination is the date of the last contact in which the participant's health status was assessed, or in cases where the participant does not agree to any further safety follow-up, it is the date consent is withdrawn. This date should be recorded on the Study Termination eCRF page.

### **3.5. Criteria for Study Termination**

The Sponsor reserves the right to terminate the study at any time. If the Sponsor or Investigator discovers conditions arising during the study that suggest the study should be halted, then study termination can occur only after appropriate consultation between the Sponsor and Investigators. Conditions that may warrant study termination include, but are not limited to:

- The discovery of any unexpected, significant, or unacceptable risk to the participants enrolled in the study.
- Failure of the Investigator to enter participants at an acceptable rate.
- Insufficient adherence to the protocol requirements.
- A decision on the part of the Sponsor to suspend or discontinue development of study drug.
- Regulatory authority request.

Should the study be closed prematurely, all study materials (study drug, etc.) must be returned to the Sponsor or designee (or disposed of as directed by the Sponsor or designee).

## 4. SELECTION AND WITHDRAWAL OF PARTICIPANTS

This study will enroll healthy male and female participants aged  $\geq 18$  and  $\leq 45$  years at Screening.

Participants will be required to meet all of the inclusion criteria and none of the exclusion criteria in order to be eligible for study enrollment; the Sponsor will attempt to reach an overall preferred combined target enrollment goal of  $\geq 30\%$  and  $\leq 50\%$  African-American and/or West African adult participants in order to help assess potential population differences in safety, tolerability and PK in the primary clinical population. In addition, the Sponsor will attempt enroll  $\geq 30\%$  and  $\leq 50\%$  female subjects to ensure adequate representation of both sexes.

In the event a participant's screening laboratory value is outside the acceptable range, the laboratory test can be repeated once, and if the repeat value is within the acceptable range, the participant can be considered eligible for the study. In the event a participant fails to meet the overall screening criteria, the participant may repeat the overall screening process once, and if the participant then meets all eligibility criteria, the participant will be considered eligible to enter the study.

### 4.1. Participant Inclusion Criteria

Participants meeting all the following criteria are eligible for study participation:

1. Is male or female, age 18 to 45 years, inclusive, at Screening.
2. Body mass index (BMI) between 18 and 35 kg/m^2, inclusive, at Screening.
3. In good general health, determined by no clinically significant findings in the opinion of the Investigator from medical history, physical examination, 12-lead ECG, clinical laboratory findings, and vital signs at Screening and Day -1 or 1.
4. Hemoglobin, hematocrit, white blood cell count, absolute neutrophil count, and platelet count results within the laboratory reference range at Screening or without clinically significant abnormalities in the opinion of the Investigator; participants with Gilbert's disease with associated abnormalities of liver function tests are eligible for enrollment. Tests may be repeated at the discretion of the Investigator to confirm abnormalities.
5. Estimated glomerular filtration rate (eGFR) based on the Chronic Kidney Disease Epidemiology Collaboration (CKD-EPI) equation of  $\geq 80$  mL/min/1.73 m^2 at Screening.
6. Females of childbearing potential must practice effective contraception per national regulatory guidelines for clinical trials from Screening (see Section 5.6.2), throughout the study, and for 60 days after the last dose of study drug.
7. Females must have a negative pregnancy test at Screening and within 24 hours prior to dosing of study drug; for post-menopausal participants, a blood sample will also be tested for estradiol and follicle stimulating hormone (FSH) to confirm post-menopausal status based on reference laboratory ranges for post-menopausal status. Surgically sterile females are eligible; however, proof via medical records will be required.
8. Males must agree to not donate sperm and to use condom and spermicide in combination with any of the means of contraception for their female partners detailed in Section 5.6.2 during sexual intercourse from the time of the first study drug administration and for

90 days following the last dose of study drug. Females must agree not to donate eggs from the time of the first study drug administration and for 60 days following the last dose of study drug.

9. Must be willing and able to comply with measures to avoid photosensitivity reactions (i.e., avoidance of outdoor sun exposure and tanning; consistent use of long sleeve shirts, long pants, hats, and sunglasses; consistent use of sun protection factor [SPF] 75 or greater sunscreen when outdoors) during the study treatment period.
10. Able to consume a standard meal (400-600 Calories) within 30 minutes.
11. Able to provide informed consent.
12. Willing and able to comply with this protocol and be available for the entire duration of the study.

